7.3.2. Alcohol calendar– Time-Line Follow-Back

Time-Line Follow-Back (TLFB) is a method that can be used to obtain information about patients' alcohol consumption. (Sobell, Maisto et al 1979). In short, it means that as far back as 3 months ago, you retrospectively reconstruct how many standard glasses you have consumed per day. It is accepted that the reporting is not an exact representation of the alcohol intake, but also that it

provides a decent benchmark, which is also sensitive to changes in the drinking pattern. An alcohol calendar (see Appendix C) is used for this purpose. For study purposes, alcohol consumption reported via TLFB is used for the 4 weeks preceding each visit. How to determine the TLFB at baseline is stated in section 8.1.2.

When filling in TLFB, the patient and therapist must consult and results of blood tests and for the intervention arm, TripleA measurements must also be taken into account to identify if and when alcohol intake has occurred.

Information about missed measurements or measurements that show alcohol in the exhaled air (both for TripleA and for regular measurements at the care provider) should be used in the TLFB call and should in the alcohol calendar correspond to a number greater than 0 standard glasses on the current day. There may be discrepancies between what the patient is willing to state in the TLFB and the information that the caregiver has available in the TripleA caregiver portal or from other sources. The caregiver should talk to the patient about this, and give the patient the opportunity to update the information in the TLFB if necessary, but should not force the patient to enter a number greater than 0 or change information provided by the patient without the patient's consent.

In CRF, it is possible for the care provider to state whether there are signs of alcohol intake that do not correspond to reported intake in TLFB.

Time: At each visit.

AUDIT (The Alcohol Use Disorders Identification Test)

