7.3.12. TripleA

Random measurements of alcohol in exhaled air, with identity control via mobile camera. Made on request via notification in mobile app - only in the TripleA arm. Reporting of results to the therapist takes place via the caregiver portal.

Timing: Sleep breaks can be added by a therapist. Thereafter, the alcohol tests take place according to schedule daily just before and after the sleep break. A third alcohol test will take place during the waking time between the 2 previous tests. If desired, this can be planned to happen randomly.

The care provider checks the care portal before each patient visit, but does not have continuous supervision of the system within the framework of the study, which is technically but not organizationally possible.

In order for TripleA to always be usable, the mobile phone has been provided with a subscription that allows free calls and SMS, as well as data traffic up to 1GB per month. Kontigo Care is responsible for the subscription fee. The patient can use the phone during the study at no extra cost.

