patient-reported data in TLFB form. If there are 3 positive blows in one day, it is very likely also a heavy drinking day (≥ 4 standard glasses / day for women, ≥ 5 standard glasses / day for men), which is medically serious. If there are alcohol tests performed in the evening 3 different days with just over 0.2 %, it can correspond to 2 glasses of wine for dinner - which can be completely acceptable if the goal is to reduce drinking and its somatic and psychological consequences (risk reduction). If you detect around 0.2 % in the morning 3 different days, it can be serious and very well mean 3 heavy drinking days where the alcohol consumption took place after the last alcohol test in the evening and the body did not have time to burn all alcohol before the next test in the morning.

The second thing to deal with is missed alcohol tests. These may be due to the patient being sober but for various reasons not being able to perform the alcohol test in time (not noticed the notification, flight, mobile data shadow, etc.) or relapse into alcohol consumption. Here, the patient can contact the care provider (or vice versa) and clarify what happened.

The caregiver has the opportunity to enter a new classification for an individual test in the caregiver portal, which means that the database will contain supplementary information - without overwriting the basic status. The following options are available for missed tests:

- No alcohol
- Alcohol could not be excluded
- Technical issue.

If the default status is "Alcohol could not be excluded", the following status comments can be selected:

- No alcohol
- Technical issue.

If the basic status is "Technical error", the following status comments can be selected:

- No alcohol
- Alcohol could not be excluded

The patient also has an opportunity to show that they have not had a relapse by submitting blood samples for analysis of PEth and CDT. The caregiver can then reclassify the missed alcohol tests as above.

Even if the caregiver indicates a new classification on a test performed or missed, the original data always remains, which is so that the percentage sobriety can be calculated in two ways:

- o Proportion of sober tests based on all alcohol tests performed.
- o Corrected proportion of sober tests where both performed and missed alcohol tests are taken into account, with the classification made by the care provider as above.

9.1.3.Explorative analyses

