We will initially summarize data from the TripleA alcohol tests as the proportion of sober days (both based on tests performed and corrected values (as above)) over a 4-week period immediately before a visit (1, 2, 3, 6.11 months). A positive alcohol test is > 0.10 mg / L alcohol in the breath test. The effect will be calculated against TLFB data transformed in a similar way. We will also perform correlation studies between TripleA and reported levels of PEth and CDT in blood samples.

The primary and secondary efficacy measures analyzed based on TLFB data will be compared with corresponding analyzes that also take into account blood test data and TripleA results.

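### The calendar rule in 7.3.2 makes no exception for the post-waking test, so one reported drinking evening can be recorded as two drinking days, mainly in the TripleA arm

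*Combined protocol and SAP*

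**What the plan says.** Section 7.3.2 governs the Time-Line Follow-Back (TLFB) calendar. Patient and therapist complete it together, and in the intervention arm "TripleA measurements must also be taken into account to identify if and when alcohol intake has occurred". A measurement that shows alcohol "should in the alcohol calendar correspond to a number greater than 0 standard glasses on the current day". The rule applies "both for TripleA and for regular measurements at the care provider", so it formally covers both arms. It is not absolute: the caregiver "should not force the patient to enter a number greater than 0" and may not alter an entry without consent. The CRF has a place to record signs of intake that do not match the calendar.

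Section 7.3.12 says that, in the TripleA arm, "the alcohol tests take place according to schedule daily just before and after the sleep break", with a third test in between.

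Section 9.1.2.2, in the item on positive and missed tests, discusses readings of about 0.2 per mille on three mornings. It says these can "very well mean 3 heavy drinking days where the alcohol consumption took place after the last alcohol test in the evening", with the alcohol not yet eliminated by the morning test.

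Section 9.1.3 will "summarize data from the TripleA alcohol tests as the proportion of sober days" over four weeks and compare the result with TLFB data. It does not say to which day a morning positive belongs, and no other section does.

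**The concern.** The purpose given in 7.3.2 is to establish whether and when drinking took place. The only dating instruction points to the day of the test, while 9.1.2.2 recognises that a morning positive may belong to the evening before. Suppose a patient correctly reports drinking on Friday evening and tests positive on waking on Saturday. On its face the rule asks for a non-zero entry on Saturday as well, a day on which nothing was drunk.

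The status comments in 7.8.3.2 do not resolve this. A positive result can be re-labelled only as no alcohol or as a technical issue, and neither describes a true reading left over from the previous evening.

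Two secondary endpoints in 7.2.2 depend directly on the number of drinking days: drink-free days, and glasses per drinking day. Comparing with baseline does not remove the artefact, because TripleA is handed out at visit 1 and the baseline calendar covers an earlier period. Time to relapse in 9.1.2.2 may use TripleA data, so a relapse seen only in a morning test may be dated one day late.

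This differs from the detection bias discussed in 7.8.11. Better detection reveals drinking that happened; this can add a drinking day that did not.

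**Working it through.** **Plan's own per-day figure.** Section 9.1.2.2 gives 29/30, printed as 96.6%, for one positive day in a 30-day month. Take one evening that is positive at the evening test and again on waking. Dated by test day it gives 28/30 = 93.3%. With the morning positive assigned to the evening before it gives 29/30. The dating choice is worth 1/30, or 3.3 percentage points, per such evening.

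**Calendar counts.** Inputs from the documents: a 28-day window, a sober day as a zero-glass day, and glasses per drinking day as total glasses divided by drinking days (7.2.2). Assumed inputs: *k* isolated evenings of *g* glasses, all correctly reported; a share *q* followed by a positive post-waking test; the patient agrees each time; and 1 glass is entered on the extra day.

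- Drinking days = k(1 + q)
- Sober days = 28 − k(1 + q)
- Total glasses = kg + kq
- Glasses per drinking day = (g + q)/(1 + q), or g/(1 + q) if the evening's glasses are spread over both dates so that the total is kept

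| k, g | q | Drinking days | Sober days | Total glasses | Per drinking day, 1 glass added | Per drinking day, total kept |
|---|---|---|---|---|---|---|
| 4, 8 | 0 | 4 | 24 | 32 | 8.0 | 8.0 |
| 4, 8 | 25% | 5 | 23 | 33 | 6.6 | 6.4 |
| 4, 8 | 50% | 6 | 22 | 34 | 5.7 | 5.3 |
| 4, 8 | 100% | 8 | 20 | 36 | 4.5 | 4.0 |
| 8, 6 | 0 | 8 | 20 | 48 | 6.0 | 6.0 |
| 8, 6 | 25% | 10 | 18 | 50 | 5.0 | 4.8 |
| 8, 6 | 50% | 12 | 16 | 52 | 4.3 | 4.0 |
| 8, 6 | 100% | 16 | 12 | 56 | 3.5 | 3.0 |

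The rows with q = 0 are what a control patient with the same drinking would show, having no daily morning test.

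**Consecutive evenings.** Within a run, each morning positive falls on a day that is already a drinking day. Only the morning after the last evening adds one, so L evenings become L + 1 days: 1 to 2, 2 to 3, 3 to 4, 7 to 8. The ratio falls from 2.0 to 1.14.

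**Primary endpoint.** A heavy day needs at least 4 glasses (women) or 5 (men), and the rule asks only for more than 0. An extra small entry creates no heavy day, and moving a heavy day within the window does not change whether there was one. Two exceptions remain. An evening of 6 glasses recorded as 3 + 3 falls below both thresholds, though the rule does not ask for a split. A carry-over entry may also fall just inside the window edge. Complete sobriety is exposed only at that edge.

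**Sample size.** The 42 per group for 30% versus 60% (two-sided 5%, 80% power, pooled variance) reproduces, and 42/0.8 = 52.5 gives 53 per group and 106 in total. None of this depends on calendar dating.

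**The case against.** The strongest reply is that 7.3.2 describes a negotiated self-report, not an automatic entry. A reader might infer that every morning positive is written in as a second drinking day. The text does not say so. The entry is something that should happen, the patient may decline, and the conversation is about when drinking occurred, which is where Saturday's reading can be explained. This stands and limits how often the error arises. It does not supply a dating rule.

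The words rendered as the current day may also mean the day in question, that is, the day of intake; the English text shows traces of machine translation. On that reading there is no contradiction. But therapists could then read the rule in two ways, so it still needs settling.

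Section 9.1.2.2 states a possibility only, and it equates three morning positives with three drinking days, not six. The authors evidently understood carry-over, but nothing brings that understanding into 7.3.2.

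The morning test is itself less certain than 7.3.12 suggests, because 7.6.1 describes notifications as random outside the night break. A reading must also exceed the 0.10 mg/L cut-off in 9.1.3. Both bear on how large *q* could be.

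Finally, a simple default that assigns all morning positives to the previous day would be wrong. Items 4 and 10 of the dependence questionnaire in Appendix B ask about drinking in the morning, and 7.6.1 allows 60 minutes to complete a test. A denied morning drink cannot be assumed rare. If the evening before is already above 0, that default would lose a real drinking day altogether. This objection stands and shapes the fix.

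**Conclusion.** The point holds as a gap in the dating rule. Followed as written, and with the patient's agreement, 7.3.2 can turn a reported isolated evening into two drinking days and a run of L evenings into L + 1. It arises mainly in the TripleA arm. It is not confined to that arm, since clinic breath tests fall under the same rule, but only TripleA patients have a daily morning test.

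A reader might infer that the error simply works against TripleA. The documents do not support that. Sober days move against TripleA and glasses per drinking day move in its favour; total intake rises slightly if glasses are added. Nor is the primary endpoint at risk beyond the two exceptions shown. For 9.1.3 no error is demonstrated; the day attribution is undefined.

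In the illustrations, one to four sober days are lost out of 24, or two to eight out of 20. These ranges rest on an assumed 25% to 100% of evenings followed by a positive morning, full patient agreement and isolated evenings only. They are not estimates for this trial. The change is still worth making, because the affected secondary endpoints are compared between arms with unequal exposure to the rule.

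**What to change.** Reconcile 7.3.2 with 9.1.2.2 by amending 7.3.2:

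- A positive test at or soon after waking is satisfied by more than 0 glasses on either the test day or the preceding evening, as established with the patient.
- No extra drinking day is required if the preceding evening is already above 0 and the patient reports no drinking since waking.
- The same rule applies to clinic breath tests, and so to both arms.

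In 9.1.3, report the TripleA sober-day proportion under two datings: by test day, and with morning positives assigned to the previous day.

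The cost is a few sentences in 7.3.2 and one in 9.1.3. The TripleA database already logs measurements, and the sleep break is set in the system. Sample size, visits and treatment are untouched. The downside is that a denied morning drink after a reported drinking evening would not count as a separate TLFB day. The CRF field for signs of intake that do not match the calendar, and the two-way TripleA count, limit that loss.

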7.3.3. DUDIT (The Drug Use Disorders Identification Test)

DUDIT (Appendix E) has been developed as a parallel instrument to AUDIT, with the aim of assessing whether problems with drugs (including addictive drugs) occur. Based on aggregated points and the distribution of these, the instruments provide information on consumption levels, signs of addiction development and injuries related to consumption.

Time: Made at visit 1

7.3.4. Questions about motivation and belief in one's own ability

The intention is to measure how motivated the patient is to change their drinking and whether it is the patient's own initiative or pressure from other parties that is behind it. The patient may also value confidence in their own ability to succeed with the change. The patient's own confidence in their ability has been shown to be predictive of treatment outcome, and a simple instrument with only one question has better predictive ability than more complex instruments (Ludwig et al, 2013). The questionnaire can be found in Appendix F.

Time: Made at visit 1

7.3.5. CGI (Clinical Global Impression) Severity and Improvement Scales

CGI is an abbreviation for Clinical Global Impression, which has been translated as "overall clinical impression".

CGI-Severity (CGI-S) means that the caregiver makes an assessment of the severity of the disease based on the question: "In the light of your clinical experience of this particular patient population, how seriously mentally ill is the patient currently?"

An answer option can be specified:

- Not assessed
- Normal, not sick at all
- Limit cases for mental illness
- Mildly ill
- Moderately ill
- Significantly ill
- Seriously ill
- Among the most extremely ill patients

Time: Done at visit 1

The initial CGI-S assessment then forms the basis for assessing whether the patient has improved or deteriorated, as indicated on the Clinical Global Impression - Improvement Scale (CGI-I) which is a scale from 1-7 where 1 corresponds to "significantly improved", 2 "much improved", 3 "slightly better", 4 "unchanged", 5 "slightly worse", 6 "much worse", and 7 "significantly worse".

CGI-I is done at visits 5 and 6.

7.3.6. EQ-5D

The EQ-5D is a standardized instrument for measuring and describing health outcomes. The EQ-5D contains a descriptive questionnaire and a vertical visual analog scale (EQ VAS).

The descriptive questionnaire in EQ-5D consists of questions where the individual can classify their own health in five different dimensions: mobility, hygiene, main activities, pain / discomfort and fear

/ depression on a three-point scale (no, moderate and severe discomfort). The individual's answers to these questions form a health profile that represents a specific health condition.

There are a total of 243 possible combinations of health conditions. On the thermometer-like scale (EQ VAS), the individual can describe how good or bad he feels by putting a cross on the scale from 0 to 100. Where 0 is the worst possible health and 100 is the best possible health. In this way, EQ VAS generates an individual self-rated state of health, so-called VAS score.

Time: Made at visits 1, 5 and 6.

7.3.7. Biological samples (blood and urine)

Samples are ordered via the medical record system, taken and handled according to regular clinical routine. Patients are instructed to leave the samples some week before the visits, so that test results are available for the visit.

For sampling instructions, refer to the latest updated versions on the Academic Laboratory's website.

Urine samples for drug screening usually include amphetamine, benzodiazepines, burprenorphine, cannabis, cocaine, methadone metabolites, opiates. Verification analysis in the event of a positive result on a urine dipstick is performed if clinically relevant

Time: Done at visit 1

Phosphatidylethanol (PEth) is analyzed at Karolinska Laboratory. The concentration of PEth-16:0/18:1 is given in the unit $\mu\text{mol} / \text{L}$. The PEth level in the blood reflects the alcohol consumption of recent weeks. PEth-16:0/18:1 values lower than $0.05 \mu\text{mol} / \text{L}$ indicate no or low sporadic alcohol consumption. Values between $0.05-0.30 \mu\text{mol} / \text{L}$ speak for regular moderate consumption, but even occasional very large intakes of alcohol can probably give measured values in this range.

Time: Made at each visit

Low carbohydrate transferrin (CDT) shows alcohol-induced change in the glycosylation pattern of transferrin, which is measured in serum samples. CDT is used as a marker to demonstrate regular alcohol consumption and «risk use / abuse», where the measured value reflects the intake during the last weeks - the month. Single major alcohol intakes do not affect CDT levels.

Analyzed at the Academic Laboratory and reported in%. Reference interval $<2.0\%$.

Time: Made at each visit

7.3.8. The assessment phase

The assessment phase must be documented in CRF with the date of the assessment interview and whether the patient chooses to continue with any type of treatment. If the patient refuses treatment efforts, the patient's participation in the study must be terminated.

Time: At visit 1 and while the assessment phase is ongoing.

7.3.9. Conventional treatment

The treatment interventions that have begun, are ongoing or have ended must be documented in CRF. Start date, end date and scope must be stated for psychosocial interventions. For medicinal products, the substance, dosage form, route of administration, strength and dose frequency and start and end dates are indicated. Time: Made at each visit.

7.3.10. Treatment goal

The goal of the treatment ("To become alcohol-free" or "To reduce alcohol consumption") is documented at visit 1 and any changes in goals are followed up at each visit. If the goal is to reduce alcohol consumption, a target level is documented. At each visit, the caregiver also makes an assessment of whether the patient has achieved his or her own treatment goal or not.

7.3.11. Compliance with treatment and meeting participation

In cases where the caregiver and patient have agreed that the patient should participate in certain activities, such as relapse prevention courses or AA meetings, compliance with this plan will be evaluated. The ratio between the number of occasions the patient participated relative to the planned number is calculated and expressed as a percentage. The calculation is made per type of activity, eg: • The number of treatment meetings that the patient has participated in the last four weeks divided by the number of planned treatment meetings for the corresponding period. • The number of AA meetings visited in the last four weeks divided by the agreed number of AA meetings the patient would have attended for the corresponding period. Time: Done at visits 2, 3, 4, 5 and 6.

7.3.12. TripleA

Random measurements of alcohol in exhaled air, with identity control via mobile camera. Made on request via notification in mobile app - only in the TripleA arm. Reporting of results to the therapist takes place via the caregiver portal.

Timing: Sleep breaks can be added by a therapist. Thereafter, the alcohol tests take place according to schedule daily just before and after the sleep break. A third alcohol test will take place during the waking time between the 2 previous tests. If desired, this can be planned to happen randomly.

The care provider checks the care portal before each patient visit, but does not have continuous supervision of the system within the framework of the study, which is technically but not organizationally possible.

In order for TripleA to always be usable, the mobile phone has been provided with a subscription that allows free calls and SMS, as well as data traffic up to 1GB per month. Kontigo Care is responsible for the subscription fee. The patient can use the phone during the study at no extra cost.

7.3.13. Safety reporting

Patients in the TripleA arm should be asked at each visit if there have been any incidents related to the use of TripleA.

Alcohol-related hospitalization since the previous visit must be noted in CRF for all study participants.

Time: Made at each visit.

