5.4. Risks associated with participation in the study

A safety aspect that should be taken into account for the relevant patient group is that an abrupt release of alcohol in people who have had a long-term and high consumption of alcohol is associated with a risk of severe withdrawal symptoms, which can be life-threatening. However, this is not linked to the use of TripleA per se, but a consequence of the release of alcohol.

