5.6. Risk reduction measures

Usual clinical procedures must be applied to manage the risks of discontinuation of alcohol and can e.g. be about gradual reduction of alcohol intake or hospitalization for detoxification.

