In the first population, missing values will be handled primarily according to the principle of multiple imputation (MI). In this approach, the missing values according to type 1 in the list above will be directly imputed according to the MI principle while values of type 2 in the list above, i.e. which are collected after treatment interruption, will remain as missing values, which are then imputed. Missing values of type 3 in the list above, ie. incompletely completed alcohol intake data, are replaced according to the principles described for each variable in section 8.3, ie. in these situations there is data and thus MI does not need to be used. For missing values of type 4 in the list above, MI is used.

In addition to the MI approach, any exploratory analyzes will be made where the principle of last-observation-carried-forward (LOCF) can be used, as well as an analysis where only observed values are included in the evaluation.

In addition to the above, a separate evaluation will be made for patients according to type 2 in the list above where collected values after treatment interruption are used. When tabulating alcohol intake data from visit 1 to visit 6, this group will be reported on three lines where line 1 indicates the number of patients in this group who remain on the treatment at each visit, while line 2 indicates the number of patients in this group who discontinued treatment from each visit. The third row then constitutes the sum of row 1 and row 2, i.e. the whole group of patients in the active group who discontinued treatment at some point after visit 1 but still remained in the study.

The analyzes performed on the ITT population will be considered as the primary ones.

The safety assessment will be based on the ITT population.

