17.1. Definitions

17.1.1. Adverse Event (AE)

An adverse medical event, accidental illness or injury, or adverse clinical signs (including an abnormal laboratory finding) in subjects, users or other persons, whether or not the event is related to the evolving medical device.

NOTE 1: This includes events related to the test product or comparison product.

NOTE 2: This includes events related to the procedures involved (all procedures in the study protocol)

NOTE 3: For users and other people, this is limited to events related to the test product.

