Appendix A

Alcohol use syndrome according to DSM-5

A problematic pattern of alcohol use leading to clinically significant impairment or suffering, manifested in at least two of the following over a 12-month period:

1. Often drink alcohol in larger quantities or for a longer period than intended.
2. There is a persistent desire or unsuccessful attempt to limit or control drinking.
3. A lot of time is spent acquiring alcohol, drinking alcohol or recovering after drinking alcohol.
4. Alcohol craving, or a strong desire or longing to drink alcohol.
5. Repeated drinking which leads to the person failing to fulfill his duties at work, at school or at home.
6. Continued drinking despite constant or recurring problems of a social or interpersonal nature caused or exacerbated by the effects of alcohol.
7. Important social activities, occupational or leisure activities are abandoned or reduced due to drinking.
8. Repeated drinking in situations where it entails significant risks of physical harm.
9. Drinking continues despite knowledge of persistent or recurrent physical or mental disorders that are likely to be caused or exacerbated by alcohol.
10. Tolerance, defined as either of the following:
 - a. Need for significantly increased amount of alcohol to achieve intoxication or other desired effect.
 - b. Significantly reduced effect with continued consumption of unchanged amount of alcohol
11. Abstinence, as manifested in either of the following:
 - a. An abstinence syndrome that is typical of alcohol (see criteria A and B for alcohol abstinence below).
 - b. Alcohol (or a similar substance, such as a benzodiazepine preparation) is used for the purpose of relieving or avoiding abstinence symptoms.

Alcohol abstinence according to DSM-5 (excerpt only criteria A and B, not complete text).

- A. The person has stopped or reduced long-term and intense alcohol use.
- B. At least two of the following have developed within a few hours to a few days after cessation (or reduction) of alcohol consumption according to criterion A:

Autonomic hyperactivity (eg sweating or heart rate above 100 beats / min).

- 2. Increased hand tremor.
- 3. Sleep disturbance.
- 4. Nausea or vomiting.
- 5. Transient visual, tactile or auditory hallucinations or illusions.
- 6. Psychomotor agitation.
- 7. Anxiety.

8. Generalized tonic-clonic seizures.

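### Section 7.3.13 gives no collection step in either arm for general adverse events or for withdrawal short of admission, so the section 17.1 definitions are not put into effect

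*Combined protocol and SAP*

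**What the plan says.** Section 7.3.13 contains two collection rules. The first applies to one arm and one kind of event: "Patients in the TripleA arm should be asked at each visit if there have been any incidents related to the use of TripleA". The second applies to everyone: "Alcohol-related hospitalization since the previous visit must be noted in CRF for all study participants".

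The definitions are wider. Section 17.1.1 counts an adverse event "whether or not the event is related to the evolving medical device", and section 17.1.5 defines a serious event by its outcome, with no restriction by arm. Section 9.2 states: "The safety assessment will be based on the ITT population". That population is drawn from all randomized patients, so it covers both arms. No safety endpoint or method of comparison is given.

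Section 5.4 says that abrupt cessation after long, heavy drinking "is associated with a risk of severe withdrawal symptoms, which can be life-threatening", and attributes this to stopping alcohol rather than to TripleA. Appendix A gives the timing in its withdrawal criterion B: "At least two of the following have developed within a few hours to a few days after cessation". Section 5.6 lists "gradual reduction of alcohol intake or hospitalization for detoxification" among the ways of managing that risk.

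**The concern.** The definitions and the analysis population are broad, but the collection rule is narrow. Staff who follow section 7.3.13 as written would ask TripleA patients about device incidents, ask controls no event question, and note alcohol-related admissions for all. A withdrawal seizure treated without admission would not be drawn out by either rule, because the protocol itself says withdrawal is not a TripleA effect.

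This matters because withdrawal could differ by arm if the product works. Section 6.2 expects more TripleA patients to cut down markedly or become sober. Section 7.7.2 excludes patients whose CDT and PEth are normalized at visit 1, so participants enter with recent regular drinking. Section 6.4 calls safety reporting essential for catching unexpected effects, and an effect that nobody recognises as device-related can be seen only by comparing arms. Section 17.7 provides no monitoring committee.

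**Working it through.** The documents give no safety figure, so the main check sets the sections side by side.

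**1. Which events have a collection step**

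| Event | TripleA arm | Control arm | Source |
|---|---|---|---|
| Incident related to TripleA | Asked at each visit | Cannot occur | 7.3.13 |
| Alcohol-related admission | Noted in CRF | Noted in CRF | 7.3.13 |
| Drug use found in routine care | Reported, passive | Reported, passive | 17.5 |
| Withdrawal without admission | None stated | None stated | 5.4 against 7.3.13 |
| Other adverse event unrelated to the device | None stated | None stated | 17.1.1 against 7.3.13 |
| Serious event not alcohol-related and not device-related | None stated | None stated | 17.1.5 against 7.3.13 |

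The two arms differ only on device incidents. The gaps in the last three rows are the same in both.

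**2. Whether section 17 supplies the missing step.** Sections 17.2 to 17.4 set out duties for malfunction, loss of performance, labelling faults and device incidents. The form named in 17.3 is a device-incident form. Section 17.1.5 mentions an SAE reporting system, but the available text does not describe one.

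**3. Timing.** Visits fall at months 0, 1, 2, 3, 6 and 12 (section 7.3.14). The intervals are 1 − 0 = 1, 2 − 1 = 1, 3 − 2 = 1, 6 − 3 = 3 and 12 − 6 = 6 months. Withdrawal develops in hours to days, so it will usually be over by the next visit and must be asked about to be recorded.

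**4. What the shared hospitalization item can show.** The plan's own sample size comes first (section 9.2: 30% against 60%, two-sided 5%, power 80%, 20% dropout). With a mean proportion of 0.45:

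n = [1.96·√(2·0.45·0.55) + 0.8416·√(0.30·0.70 + 0.60·0.40)]² / 0.30² = (1.379 + 0.565)² / 0.09 ≈ 42 per group.

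42 / 0.80 = 52.5, rounded up to 53 per group, or 106 in total. This reproduces the plan.

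The same approximation with 53 per arm uses power = Φ{[d·√53 − 1.96·√(2·p̄(1−p̄))] / √(p₁(1−p₁) + p₂(1−p₂))}, where d = p₂ − p₁ and p̄ is their mean. The documents give no admission rates, so the rates below are assumptions:

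| Assumed admission rates | Power |
|---|---|
| 5% against 15% | (0.728 − 0.832)/0.418 = −0.25, about 40% |
| 5% against 20% | (1.092 − 0.917)/0.456 = 0.38, about 65% |
| 5% against 25% | (1.456 − 0.990)/0.485 = 0.96, about 83% |

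These are rough, since 53 × 0.05 = 2.65 expected events is a small count. If no event is seen in 53 patients, the one-sided 95% upper limit is 1 − 0.05^(1/53) = 5.5%; in 42 patients it is 1 − 0.05^(1/42) = 6.9%.

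**The case against.** The strongest reply is that all-arm reporting was intended. The safety reporting row in section 7.3.14 is marked at every visit and does not carry the intervention-arm-only sign. The visit lists in 7.8.4 to 7.8.8 send staff to section 18, which sections 6.4 and 7.8.2 label as safety reporting, so it is evidently the present section 17 with its broad definitions. Section 17.3 asks the doctor to judge causality, which suggests reporting before attribution. The CRF is not reproduced, data management is described in a separate plan, and either may hold an adverse-event page. The intention is plausible, but nothing in the protocol turns it into a question or a required record.

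Medicines with start and end dates are documented at each visit in both arms (section 7.3.9), so drug-treated withdrawal may leave a trace. That stands, but a prescription is not a recorded event.

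The product is CE-marked and studied within its intended use, which explains the device focus of section 17.2. Section 6.4 aims at risks with TripleA, and no between-arm safety test is planned. This limits the point to a gap in collection; it does not explain why the adverse events that the protocol defines go uncollected.

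Note 2 in section 17.1.5 keeps planned stays without serious deterioration out of the SAE count. That settles SAE classification, but the separate hospitalization item remains undivided.

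A reader might infer that the safety comparison is biased against TripleA because only that arm is questioned. The documents do not support this: the question concerns device incidents, which controls cannot have, and events unrelated to the device are missed in both arms. A reader might also infer that no safety comparison is possible. That goes too far, since alcohol-related hospitalization and drug use found in routine care cover both arms.

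**Conclusion.** The point holds as under-collection that is mainly symmetric between the arms. Followed as written, section 7.3.13 would leave the ITT safety assessment without general adverse events and without withdrawal short of admission, apart from indirect traces such as medication records. The arms cannot be compared on those events. They can be compared on alcohol-related hospitalization, where under the assumed rates only large differences would be found reliably, and passively on drug use.

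The hospitalization comparison would also be hard to interpret. Section 5.1 expects relapses to be noticed sooner with TripleA and further treatment to start if needed, so planned admissions could differ by arm without any difference in harm. Whether they would, and in which direction, the documents do not show.

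The conclusion rests on the protocol text. An adverse-event page in the CRF, if one exists, would narrow the gap in practice, though the protocol should still require it. The sample size is not in question. This is a low-cost improvement that should be made.

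**What to change.** Amend section 7.3.13 and the CRF as follows:

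- Ask both arms the same open question at visits 2 to 6 about any adverse event since the last visit, with a specific prompt for withdrawal based on the criterion B list in Appendix A. Record the start date, and record the event regardless of its relation to the device.
- Add a reason for each alcohol-related admission: planned detoxification, withdrawal complication, intoxication or injury, or other.
- Keep the device-incident question for the TripleA arm only, and tabulate it separately without a between-arm comparison.
- State in section 9 that AEs and SAEs are summarised by arm in the ITT population.
- Reconcile 7.3.13 with 17.1 to 17.3 by giving a route to the sponsor for SAEs unrelated to the device in either arm. Use a general SAE page, since the form named in 17.3 is for device incidents and does not fit a control patient. Correct the visit-list pointers to section 18 at the same time.

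The cost is a protocol amendment, one CRF page, a few minutes per visit and more non-device events to process. No visit, procedure or staff is added, and patient management does not change.
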